1.3 Notification of deaths

All deaths will be reported to the Sponsor irrespective of whether the death is related to disease progression, the intervention, or an unrelated event. These reports shall be made immediately.

Data management and quality assurance

Confidentiality

All data will be handled in accordance with the Data Protection Act 1998.

The Case Report Forms (CRFs) will not bear the participant's name or other directly identifiable data. The participant's trial Identification Number (ID) only, will be used for identification. The sponsor Subject ID log JREOLOG0002 can be used to cross reference participant's identifiable information.

1.2 Data collection tool

Case Report Forms will be designed by the CI. All data will be entered legibly in black ink with a ball-point pen. If the Investigator makes an error, it will be crossed through with a single line in such a way to ensure that the original entry can still be read. The correct entry will then be clearly

inserted. The amendment will be initialled and dated by the person making the correction immediately. Overwriting or use of correction fluid will not be permitted.

It is the Investigator's responsibility to ensure the accuracy of all data entered and recorded in the CRFs. The Staff Delegation of Responsibilities Log JREOLOG0004 will identify all trial personnel responsible for data collection, entry, handling and managing the database.

The raw data generated from the study will be in TIF format (as images of protein distribution) and they shall be stored, de-identified, in [name] computer at City St George's, University of London. Observations regarding protein-protein distribution will be noted in the CRF.

Incidental Findings

We are looking at the distribution of proteins at cell-cell junctions, the areas where cells are coupled together, which may only indicate a potential propensity to an arrhythmic disorder. Incidental findings are not relevant to this type of study.

Data handling and analysis

The data will be stored in TIF (images) format. The observations of the images will be logged on excel spreadsheets. City St George's, University of London is developing an institutional data repository as part of a Jisc-funded RDM Shared Service (April 2016 - September 2017). This will provide discoverability, secure storage and long-term preservation for all research data deposited in it. The PI will not have access to patient data/medical records. Slides will be labelled by a unique study participant ID code. There shall be no hard copy of the key linking the code to patients kept in the laboratory. There will be a linked document stored in the ISF JREOLOG0002. The study will be conducted in compliance with SOPs, GCP, all relevant laws of the EU and the UK including but not limited to: the Human Rights Act 1998, the Data Protection Act 1998, the Human Medicines Regulations 2012, ICH, the World Medical Association Declaration of Helsinki (2008), the NHS Research Governance Framework for Health and Social Care (2005). At the end of the study all coded samples shall be disposed of in accordance with the Human Tissue Authority's code of practice. Data generated will be kept on a password-protected workstation within a controlled-access office at City St George's, University of London. Computer softwares and firewall protection are up to date. City St George's, University of London servers are protected by line-interactive uninterruptible power supply (UPS) systems. No data will be kept in cloud-based storage. Only secure City St George's, University of London -controlled FTP servers will be used to share data with other team members. No sensitive data will be emailed according to ISO 27001. Digital data kept on City St George's, University of London servers are backed up overnight, every night, to hard disk and then cloned to tape storage. Full backups of all the data will be carried out monthly. The cloned tapes are stored separately in a fireproof and bombproof safe off-site. Laptops will be backed up and data removed from them as soon as practicable. This is in accordance with the City St George's, University of London Information Security and Removable Media policies: <https://portal.sgul.ac.uk/org/lis/computing-services/infosec-external>

Archiving arrangements

The trial essential documents along with the trial database will be archived in accordance with the sponsor SOP JREOSOP0016. The agreed archiving period for this trial will be 10 years.

Statistical design

Statistical input in trial design

Endpoints

Primary endpoints

The primary end point will be the presence of signal for a specific protein at the junctions of the buccal smear sample. No quantification of immunoreactive signal will be performed as this approach may increase bias. Accordingly, the results for each protein stain will be categorized as “present” or “absent”.

The end point of the sub-study will be whether a protein of interest is expressed at control levels or significantly decreased levels in the presence of a mutation. Accordingly, the results for each protein examined will be categorized as ‘control’ or ‘reduced’.

Secondary endpoints

Not applicable for this study.

Sample size and recruitment

Sample size calculation

The sample size was calculated based on the size of the St. George's and satellite centres' Arrhythmia Services. The number selected constitutes only a fraction of the individuals evaluated and regularly followed at the hospitals involved and will allow us to obtain statistically significant results for each arrhythmic disorder.

Planned recruitment rate

Based on the number of patients/family members evaluated at the arrhythmic services at City St George's, University of London, we estimate that we shall be recruiting approximately 200 individuals per year over the 4 year course of the study.

Statistical analysis plan

Summary of baseline data and flow of patients

The participants will include individuals from 3 groups:

1. Patients already diagnosed with an arrhythmic disorder
2. Relatives of patients diagnosed with arrhythmic disorders to establish risk status
3. Relatives of SCD victims for risk stratification.

There shall be no randomization of the participants and no differential treatment amongst the population. All individuals enrolled will only provide a buccal smear sample.

Primary endpoint analysis

Both for the primary study (buccal smear immunostaining) and the sub-study (buccal cell western immunoblotting) only frequencies and associations will be assessed. No complex statistical analysis is required for completion of this study. Differences between disease groups in the distribution of immunoreactive signals and levels of protein expression will be assessed in a pairwise fashion with the Fisher exact test. Bonferroni correction will be used to correct P values because of multiple comparisons as appropriate. A p value of less than 0.05 will be considered significant. SPSS 21.0 software shall be used for all analyses. This statistical analysis will be performed by [name]. If expert statistical help is required, the research team will consult medical statisticians within St. George's University of London ([name] [name]) who shall not have access to the participants' personal information.

To describe the precise methods of analysis, I shall use ACM as an example. We have previously shown that in the hearts of patients with ACM a protein known as plakoglobin is dislocated from the cell-cell junctions regardless of the underlying pathogenic mutation or even in cases where no mutation has been identified but the clinical or pathological examination are consistent with a diagnosis of ACM. We used the "presence" or "absence" of plakoglobin from the cell junctions in the buccal mucosa to predict which individuals had ACM in a blinded fashion. Of 39 patient samples obtained, plakoglobin was absent from the cell junctions in 34. It was not, however, absent in samples from patients diagnosed with other forms of cardiomyopathy including hypertrophic, dilated or ischemic cardiomyopathy. This indicated that using plakoglobin distribution in the buccal mucosa as a means to diagnose ACM had sensitivity of 87.1% and specificity of 100%.

Secondary endpoint analysis

Regarding the secondary outcome of the analysis: patients with ACM bear mutations in genes encoding desmosomal proteins. These include desmoplakin, desmoglein2, desmocollin2, plakoglobin and plakophilin2 (PKP2). Buccal cells do not express PKP2. Instead they express a different isoform of the protein; plakophilin1 (PKP1). 15/15 ACM patients bearing mutations in PKP2 showed loss of PKP1 signal in their buccal mucosa. No patients bearing mutations in different genes showed this abnormality. Moreover, only patients bearing mutations in desmoplakin, desmoglein2 or desmocollin2 showed loss of desmoplakin signal in their buccal mucosa. Accordingly, using PKP1 distribution to predict the presence of mutations in PKP2 showed 100% specificity and sensitivity. This is a remarkable finding given how PKP1 and PKP2 are expressed by different genes localized on different chromosomes. And yet, a mutation in one

isoform expressed in one tissue affects distribution of a different isoform expressed in a different tissue. Similarly, using desmoplakin distribution to predict the presence of mutations in desmoplakin, desmoglein2 and desmocollin2 showed 100% specificity and sensitivity. We are now at a position to use the same approach in other, more common forms of arrhythmic disorders including the cardiac channelopathies.

We shall use the presence or absence of signal for specific proteins at buccal smears to:

1. predict clinical diagnosis for heritable arrhythmic disorders
2. predict the genes bearing disease-causing mutations
3. assess the effect of potential changes in treatment plan on the distribution of proteins (specifically Cx43)

We shall use the expression levels of specific proteins to establish

1. If mutations act through haploinsufficiency
2. If anti-arrhythmic medication corrects the distribution of connexin43 by increasing its production levels.

Sensitivity and other planned analyses (if applicable)

Please see explanation above

Interim analysis

If following the first year of the study, it appears that we are unable to predict "arrhythmic status" using such samples, we shall stop recruiting patients with cardiac channelopathies and will only focus on patients with cardiomyopathies, where the correlation is already proved

Committees involved in the trial

A trial management group (TMG) will be in place throughout the duration of the study

This will include those individuals responsible for the day-to-day management of the study, such as the CI, research nurse and medical care providers. The role of the group will be to monitor all aspects of the conduct and progress of the study, ensure that the protocol is adhered to and take appropriate action to safeguard participants and the quality of the study itself.

Direct access to source data

The Investigator(s)/institution(s) will permit trial-related monitoring, audits, REC review, and regulatory inspection(s), providing direct access to source data/documents. Trial participants are

informed of this during the informed consent discussion. Participants will consent to provide access to their medical notes.

Ethics and Research Governance requirements

Before any site can enrol patients into the trial, the Principal Investigator must ensure written permission to proceed has been granted by that Trust Research & Development (R&D). If conducting the study at City St Georges contact the governance team within the JREO for any assistance.

The site must conduct the trial in compliance with the protocol as agreed by the Sponsor and, which was given favourable opinion by the Research Ethics Committee (REC).

The Chief Investigator will be provided (via the Sponsor) with file indexes E.G. JREODOC0003 TMF index and JREODOC0004 ISF index for use with SOP JREOSOP0019 'Preparation and Maintenance of the TMF' The CI will be responsible for the maintenance of the TMF and may delegate the responsibility of ISF file maintenance to the PI at each participating site.

It is the responsibility of the Principal Investigator to ensure that all subsequent amendments gain the necessary approval. Refer to JREOSOP0011 'Management of Amendments'.

Within 90 days after the end of the trial, the CI and Sponsor will ensure that the REC is notified that the trial has finished. If the trial is terminated prematurely, those reports will be made within 15 days after the end of the trial. Refer to JREOSOP0015 'End of study declaration'

The CI will supply an End of Study report of the clinical trial to the REC within one year after the end of the trial. The sponsor can provide JREODOC0059 End of study Report template

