Identifiable		
*Pseudonymised		
Anonymised		

**Confirm that the key to this data is kept securely away from the used data with strict controlled access*

The key linking the study ID number to a specific participant will be held in secure workstations at or Bart's Hospital, only accessible by the participant's regular medical team.

List all organisations / agencies which will have access to the personal data collection used for this project / process

Only the regular medical care providers of each participant will have access to the participants' personal data. No personal data will be collected for the purpose of this study.

Length of the study – include an assessment of the necessity and proportionality of the processing in relation to the purpose. Also include who, internally & externally, has been consulted in the preparation of this DPIA.

The current end date of the study is 30/06/2026. All eligible participants have regular follow-up appointments every 6 or 12 months. In order for us to recruit enough participants for the study's outcomes to reach statistical significance, at least 1 year is required.

[name], the City St George's, University of London representative has been consulted for the preparation of this DPIA.

If external organisations / agencies are involved, is there a contract or information sharing agreement in place with suitable clauses for data protection and data incident reporting.? If not why not?

Not applicable.

RISK

Can you achieve your objectives using anonymised data? – see ICO Code of Practice on Anonymisation

Yes	X	
No		Why not?

What are the benefits to the individual of their personal data being used for this purpose?

Not applicable

What are the organisational benefits of the individual's personal data being used for this purpose?

Not applicable

What are potential negative impacts to the individual of their personal data being used for this purpose in the event of a Data Breach occurring?
 
Not applicable
											

How will you avoid causing unwarranted or substantial damage/distress to the individual when using their personal data for this purpose?
 
Not applicable
											

Is the data already held by City St George's?
 
 
 Yes	X		
 
 No			
 
				Yes	X			No			

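### The target of 800 is said to secure significance for every disorder without statistical support, and no planned analysis compares patients with the clinically unaffected relatives whom cascade screening is meant to serve

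*Combined protocol and SAP*

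**What the plan says.** **Sample size.** Under Sample size calculation (14.3) the plan states: "The sample size was calculated based on the size of" the St. George's and satellite arrhythmia services. It adds that the number "will allow us to obtain statistically significant results for each arrhythmic disorder". Planned recruitment rate gives about 200 people a year for four years.

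**Analysis.** Under Primary endpoint analysis, "only frequencies and associations will be assessed". The one named test is Fisher's exact test, applied pairwise to "Differences between disease groups in the distribution of immunoreactive signals" and in expression levels, at 0.05. On multiplicity: "Bonferroni correction will be used to correct P values because of multiple comparisons as appropriate". The number of comparisons is not given, and Laboratory procedures (10.5.1) leaves the list of proteins open.

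**Worked example.** Absence of junctional plakoglobin was found in 34 of 39 ACM samples. For specificity the plan says: "It was not, however, absent in samples from patients diagnosed with other forms of cardiomyopathy including hypertrophic, dilated or ischemic cardiomyopathy". The denominator is not given.

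**Relatives.** Inclusion criteria (7.1) and Screening assessments (10.1) admit family members with or without disease manifestation. Two of the three participant groups in the analysis plan are relatives. Primary objective (5.1) covers both diagnosis and cascade screening, including silent carriers. Secondary endpoint analysis lists prediction of the clinical diagnosis and of the mutated gene.

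**The concern.** There are two linked gaps.

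First, a number chosen for feasibility is presented as securing significance for each disorder. A reader who accepts this could take a null result in a channelopathy as evidence of no association, when the group may have been too small to show a moderate one.

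Second, a screening test is judged by how often it is abnormal in people without the disease. The plan enrols clinically unaffected relatives but gives them no place in a comparison. Its specificity would therefore be against other heart diseases. Disease-versus-disease testing also cannot reveal a marker that is altered equally in the disorders compared, even if that marker separates disease from no disease.

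**Working it through.** **1. The plan's own figures.** 200 a year × 4 years = 800, so the recruitment arithmetic holds. Pilot sensitivity is 34/39 = 87.2% (the plan prints 87.1%), exact 95% CI 72.6% to 95.7%. The claim of significance cannot be reproduced, because no power, expected rate or group size is given.

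**2. Number of tests.** Inclusion criteria name seven disorders, giving 7 × 6 / 2 = 21 pairs. With the four proteins named in Laboratory procedures, 21 × 4 = 84 tests. Bonferroni thresholds are 0.05/21 = 0.00238 and 0.05/84 = 0.000595.

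**3. Group sizes (assumed).** If all 800 were diagnosed patients split equally, 800/7 ≈ 114 per disorder. If one third were diagnosed patients, 800/3/7 ≈ 38. The plan gives no split.

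**4. Power of the two-sided Fisher test, by full enumeration.** Power is the sum over all pairs (x₁, x₂) of Bin(x₁; n, p₁) × Bin(x₂; n, p₂), counted where the Fisher p-value is below the threshold. The 87% comes from the pilot. The 5%, 50% and 20% are assumptions.

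| Rates | n per group | 0.05 | 0.05/21 | 0.05/84 |
|---|---|---|---|---|
| 87% vs 5% | 15 | 99.9% | 97% | 92% |
| 50% vs 20% | 38 | 73% | 32% | 18% |
| 50% vs 20% | 114 | 99.7% | 95% | 90% |

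For 50% vs 20%, 80% power needs 44, 80 or 95 per disorder at the three thresholds. Over seven disorders that is 308, 560 or 665 diagnosed patients, in a study where two of three participant groups are relatives.

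**5. A shared marker.** With 80% abnormal in both disorders (assumed), the test rejects at 0.05 in 2.7% of studies with 38 each and 3.5% with 114 each. Any valid test behaves this way under equal rates. The point is that more patients do not help, because the contrast is the wrong one for such a marker. The synopsis reports Cx43 remodelling in ACM, dilated and hypertrophic cardiomyopathy. These form 3 of the 21 pairs. No rates are given, and no Cx43 result is given for the channelopathies.

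**6. What unaffected relatives could give.** With no false positives among n independent relatives, the exact lower 95% limit for specificity is 0.025^(1/n): 83% for n = 20, 91% for 38 and 96% for 100. With design effect 1 + (m − 1) × ICC, an assumed m = 3 relatives per family and ICC 0.5 give 2. The effective numbers are then 10, 19 and 50, and the limits 69%, 82% and 93%. For one disorder (38 patients) against 20 independent relatives at 0.05/28 (7 disorders × 4 proteins), an assumed 80% vs 10% has 99% power. An assumed 50% vs 20% has only 14%, and 28% with 38 relatives.

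**7. Expected precision of sensitivity.** 99/114 gives an exact 95% CI of 79% to 92%; 33/38 gives 72% to 96%.

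**The case against.** The strongest reply is that every contrast the documents report is very large: 34 of 39 against none for ACM, and 15 of 15 against none for PKP2 mutations. At that size 15 per group is enough, and only the assumed 50% vs 20% produces weak power. This stands. A reader might infer that the study is underpowered, but the documents give neither the effects nor the group sizes needed to say so.

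It can also be said that the plan does not lack a reference standard. Inclusion criteria classify family members as affected or as carriers on conventional cardiac tests, and Secondary endpoint analysis plans to predict clinical diagnosis. The worked example likewise accepts a clinical or pathological diagnosis "or even in cases where no mutation has been identified". This stands too. A usable standard is written down; what is missing is its assignment to an analysis of unaffected relatives. The allowance for frequencies and associations would permit describing them, but it names no comparison.

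Three further inferences go too far:

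- The DPIA (section 25) says that for "outcomes to reach statistical significance, at least 1 year is required". This is a minimum time without a calculation. It does not say that one year's recruits suffice, so no power figure should be set against it.
- One might assume that a group of relatives who tested negative for the family variant is available. Inclusion criteria describe unaffected relatives as potential carriers, and Participant Recruitment process selects those thought to be at risk. Such a group is not established.
- Subsequent assessments (10.4) asks everyone for further samples, while other sections say one sampling is enough for most. Nothing says that repeat samples enter the Fisher test.

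**Conclusion.** The concern holds in two parts. The sentence promising significance for each disorder has no statistical basis in the documents and should be called unsupported. ACM-sized effects are safe. A moderate effect ranges from 18% to 99.7% power, depending on the split of the 800 and the number of tests, neither of which is stated. Those figures rest on assumed equal splits and on an assumed 50% vs 20%.

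The second part needs no assumed rate. As written, no analysis compares patients with clinically unaffected relatives, so the study would report specificity against other diseases only, although its primary objective includes cascade screening. A marker shared by several disorders would look null between them. Intervention plan and rationale (6.2) mentions 15 unaffected carriers in the earlier ACM work, but these documents give no smear result for them, so the gap is not filled there.

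This should be fixed. It does not invalidate the disease-versus-disease comparisons already planned.

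**What to change.** 1. **Sample-size sentence.** Replace it with: *The target of 800 reflects recruitment capacity; significance for each disorder is not assured.* Add the expected precision from step 7 of the working.
2. **Added comparison.** Keep the disease-versus-disease tests. For each disorder, prespecify a comparison of patients with clinically unaffected relatives, with the clinical classification in Inclusion criteria as reference standard. Use each participant's first sample and give exact CIs for sensitivity and specificity. Allow for families, for example with one member per family in the main analysis and all members in a supporting one. Report relatives by carrier status where known:
   - known carriers as proportion abnormal, outside specificity;
   - tested-negative relatives, if any are enrolled, as the cleanest specificity estimate;
   - relatives of unknown status separately, noting that specificity there is probably understated because some may be silent carriers.

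   State that the number of tested-negative relatives is unknown and that the eligibility and recruitment wording may limit it.
3. **Multiplicity.** Define the Bonferroni family for the added comparison as disorders × proteins tested, including proteins added later: 7 × 4 = 28 now, or 6 × 4 = 24 without cardiac sarcoidosis, which Screening assessments omits. Count the retained pairwise tests explicitly as well (84 now).
4. **Data form.** Add participant group, clinically affected yes/no, carrier-test status (including tested negative and not tested) and a coded family identifier. The form items listed in the DPIA do not state these explicitly.

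**Cost.** Changes to the analysis plan and form, Sponsor and REC approval of the amendment, and recoding of earlier forms, since the anticipated start was 2017. One member per family discards some data. The sample-size statement becomes less favourable. For samples already read, the added comparison should be labelled as specified after those readings.
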